## **12. DATA AND SPECIMEN BANKING\* N/A**

### **13. Data Analysis and Management\***

All data will be double entered and linked by a common identification number across data sources. We will minimize missing data through careful checking of all surveys and data forms at the time of completion. Baseline characteristics of participants who drop out will be compared to those who complete the study.

Analyses for Specific Aim #1. The process measures of feasibility will assess attendance, degree of participant enjoyment, and participant and parental satisfaction based the aforementioned surveys. These measures will be summarized as means and proportions, with corresponding 95% confidence intervals, and compared across the two waves. If there are no important differences, we will pool across waves. We will use the 6-week and 12-week measures to assess if engagement builds, sustains or declines over the intervention period. We will also examine study completion and attendance by wave.

Analyses for Specific Aim #2a. To assess if the intervention increases aspects of physical literacy including movement competence (ability), confidence, and desire to participate in physical activity, we will conduct 1-sample paired t-tests for change (against the null hypothesis of a change of zero) in separate tests for TGMD-3 scores, PSI-VSF-ID physical self-concept, and CSAPPA score. We will construct 95% confidence intervals around the measure of change separately for boys and girls, and pool them if we discern no important differences by sex. If, based on Aim #1, we believe there were important implementation differences between the two waves, we will analyze them separately, acknowledging our power will be more limited.

Analyses for Specific Aim #2b. Analyses to assess if the intervention increases elements of food literacy (i.e., knowledge and skills) for promoting intake of fruits and vegetables and for decreasing intake of high energy low nutrient dense snack foods will proceed as for Aim #2a. We will use a 1-sample (paired) t-test to test Food Knowledge, Food Skill Master, and Dietary Behavior scores. We will construct 95% confidence intervals around the change separately for boys and girls, pooling them if we discern no important difference by sex. If, based on Aim #1, we believe that there were important implementation differences across the two waves, we will analyze them separately, acknowledging our power will be more limited.

Sample Size Considerations. We established the sample size for this pilot study based on the aforementioned total and skill score on the CAMSA (Specific Aim #2a). Using available estimates from TD adolescents, we calculated the sample sizes needed to capture a 15% change

in score for boys and girls separately (score improvements of 6.63 total; 3.66 skill). Estimates on the CAMSA from adolescents with ID are unavailable in the literature; however, we have no reason to believe that the proposed intervention would have a different impact on adolescents with ID than TD adolescents. We estimated the standard deviation of the change in the measure (5.19 total; 3.10 skill) and the interclass correlation coefficient (0.91 total; 0.80 skill), as recommended. A sample size of 12 boys and 12 girls has, at an alpha level of 0.05, 80% power to assess a difference of 15% in total score and 15% in skill score, analyzing boys and girls separately. We have proposed to enroll 15 boys and 15 girls in our pilot study to allow for attrition and or missing data. If we do not identify important differences in the change in score by sex we will combine them, with the result that we would have adequate power to detect changes of the magnitude ~5% total and skill scores.

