## **7. STUDY-WIDE NUMBER OF SUBJECTS\* N/A**

## **8. STUDY-WIDE RECRUITMENT METHODS\* N/A**

## **9. STUDY TIMELINES\***

The table on the next page depicts study activities over the two years of the project. The 12-week intervention will run remotely in three concurrent waves/cohorts of 10 participants (winter/spring 2022 through summer 2022). Conducting the intervention remotely will allow us to recruit

throughout the state of Massachusetts, which will assist in enrolling the planned number of participants (n=30).

The study was put on-hold in March 2020 due to COVID shortly after enrolling participants and commencing with the intervention. The timeline listed below illustrates our new plan.

		Year 2 Sept 1 2020 to Aug 31 2021												Year 3 – Current Year (no-cost extension) Sept 1 2021 to Aug 31 2022												
Tasks ↓	Months ⇌	S	O	N	D	J	F	M	A	M	J	J	A	S	O	N	D	J	F	M	A	M	J	J	A	
Participant-related activities suspended due to COVID-19		X	X	X	X	XX	X	X	X	X	X	X	X													
Start-up activities – hire staff, training and preparation														X	X	X	X									
Recruit, screen, & enroll participants																	X	X	X							
Data collection – baseline measures																	X	X	X							
Intervention																				X	X	X	X			
Data collection – post intervention measures																									X	
Data coding, entry & analysis																									X	X
Dissemination - presentation and manuscript preparation.																										X

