### **Physical Literacy & Food Literacy Intervention.**

The 12-week intervention is designed to expose adolescents with ID to a variety of sports skills and healthy eating concepts to equip them with skills and confidence to participate in physical activities and make healthy food choices. The proposed sport sampling and healthy eating program will follow a protocol that can be adapted to meet the needs of a diverse group of adolescents with ID. Sessions will be held weekly for an hour and fifteen minutes. One cohort will meet Thursday evenings, the second cohort will meet Saturday mornings, and the third cohort will meet at a day/time that is to be determined based on the input of participating families on other days/times that would have worked for their schedules. 35 minutes will be dedicated to sport activities followed by 35 minutes dedicated to the curriculum on healthy eating with a 5 minute break in between. All sessions will be recorded to be coded as data at a later time by graduate students.

Sport Skills Sampling. The sport skills program will be delivered remotely with modifications that promote engagement in activities at home. The program will be organized by general sport

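### Section 13 analyses two waves where three cohorts are run, and lets the observed change scores decide whether each Aim 2 result is pooled or sex-specific

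*Combined protocol and SAP*

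**What the plan says.** **Cohorts.** Section 9 states: "The 12-week intervention will run remotely in three concurrent waves/cohorts of 10 participants". Section 11, under the intervention heading, gives one cohort Thursday evenings and one Saturday mornings, and adds that "the third cohort will meet at a day/time that is to be determined".

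**Waves in the analysis.** In Section 13 the Aim 1 measures are reported "with corresponding 95% confidence intervals, and compared across the two waves", followed by "If there are no important differences, we will pool across waves". Aim 2a says that if, from Aim 1, "we believe there were important implementation differences between the two waves, we will analyze them separately". Aim 2b has the same rule: "we believe that there were important implementation differences across the two waves, we will analyze them separately".

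**Sex.** Aim 2a plans a paired t-test of change for each outcome, then 95% confidence intervals "separately for boys and girls, and pool them if we discern no important differences by sex". Aim 2b does likewise, "pooling them if we discern no important difference by sex". Under Sample Size Considerations the study is sized for boys and girls analysed separately (12 per sex, 15 enrolled). The sexes are to be combined if no important sex difference in the change in score is identified.

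**Hypothesis.** Section 4 expects significant improvement among participants as a whole and gives no sex-specific hypothesis.

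**The concern.** There are two separate matters.

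1. The wave comparison in Section 13 decides whether Aim 1 is pooled and whether Aim 2 is split. A two-wave comparison cannot be applied literally to three cohorts: the text does not say which two are meant or how the third enters.

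2. The choice between a pooled and a sex-specific Aim 2 result is made from the change scores that are then tested. The plan gives no threshold, test or margin for an important difference and names neither result as the main one. It also does not say whether the choice is made once or outcome by outcome. A reader cannot tell beforehand which estimate answers the Section 4 hypothesis. If a significant change in either sex would count as success, the error rate can exceed 5%.

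Two things are not at fault. Sex-specific analysis is planned and is the sizing basis. The Aim 2 wave split is triggered by Aim 1 implementation findings, not by the change scores.

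**Working it through.** **Cohort count.** Section 9: 3 cohorts × 10 = 30, which equals the 15 boys + 15 girls to be enrolled. All 30 places are therefore in three cohorts. Three cohorts give 3 pairwise comparisons; two waves give 1.

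**Inputs for the sex rule.** 12 per sex (evaluable) and 15 per sex (enrolled), alpha 0.05 and a one-sample paired t-test come from Section 13. Two-sided testing is assumed because sidedness is not stated. The plan gives no error rate for this rule, so there is no figure of its own to reproduce. Its power calculation is not needed here.

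**Assumptions.** The criterion for splitting is assumed, because none is given. Four were tried: non-overlapping sex-specific 95% confidence intervals (closest to the text), and a sex-difference p-value below 0.05, 0.10 or 0.20. The success rule after a split is also assumed: either sex significant, or both.

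**Method.** Null trials were simulated with normal change scores of mean zero (400,000 trials for the either-sex results). If the criterion is met, each sex is tested at 0.05; otherwise there is one pooled test.

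Two-sided error per outcome, 12 per sex:

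| Criterion for splitting | Trials split | At least one sex significant, among split trials | Error, either sex counts | Error, both sexes needed |
|---|---|---|---|---|
| Non-overlapping 95% CIs | 0.55% | 100% | 5.5% | 5.0% |
| p < 0.05 | 5.0% | 63.4% | 7.9% | 4.8% |
| p < 0.10 | 10.0% | 47.3% | 9.2% | 4.6% |
| p < 0.20 | 20.0% | 32.6% | 10.5% | 4.1% |

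The 100% holds by construction, since two non-overlapping intervals cannot both contain zero.

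**Check by hand.** Error ≈ P(split) × P(significant given split) + P(not split) × 5%.
- Non-overlap: 0.0055 × 100 + 0.9945 × 5 = 5.5%.
- p < 0.05: 0.05 × 63.4 + 0.95 × 5 = 7.9%.
- p < 0.10: 0.10 × 47.3 + 0.90 × 5 = 9.2%.
- p < 0.20: 0.20 × 32.6 + 0.80 × 5 = 10.5%.

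**Comparators.** Pooling fixed in advance: 5.0%. Both sexes always tested without adjustment: 1 − 0.95² = 9.75%. Counting improvements only, the either-sex figures are 2.8%, 4.0%, 4.7% and 5.3%, against 2.5% and 4.9%. At 15 per sex the two-sided either-sex figures are almost the same (5.5%, 7.9%, 9.2%, 10.5%).

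**One decision for all outcomes.** If the choice made on one outcome is applied to another with unrelated change, the error on that other outcome under the three p-value criteria is:
- 0.95 × 5 + 0.05 × 9.75 = 5.2%
- 0.90 × 5 + 0.10 × 9.75 = 5.5%
- 0.80 × 5 + 0.20 × 9.75 = 6.0%

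**What the sex comparison can show.** With a two-sample t-test, two-sided 0.05 and 80% power, the detectable sex difference is 1.20 SD of change (12 per sex) or 1.06 SD (15). A true difference of 1 SD would give p < 0.05 in 65% or 75% of trials, and non-overlapping intervals in only 30% or 41%.

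**Precision.** The 95% CI half-width in SD of change is t/√n:
- pooled, n = 24: 2.069/√24 = 0.42
- pooled, n = 30: 2.045/√30 = 0.37
- one sex, n = 12: 2.201/√12 = 0.64
- one sex, n = 15: 2.145/√15 = 0.55

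**The case against.** Most of the opposing case concerns weight, and much of it stands.

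- **The wave count is probably clerical.** The planned step (summarise, compare, pool or separate) works equally well with three cohorts. A reader might infer that one cohort would be left out of the analysis; nothing in the documents says so.
- **The sex sentence can be read as being about intervals only.** The Aim 2 t-tests are stated first and without a sex condition; the pooling clause is attached to the confidence intervals. On that reading the error rates do not apply. Sample Size Considerations points the other way, since it discusses power for separate and for combined analysis. The text is ambiguous, and that is itself part of the point.
- **Inflation needs a success rule the plan does not contain.** A reader might infer a material type I error failure. The documents do not support that: they nowhere say that significance in one sex is enough, and requiring both removes the inflation. Under the criterion closest to the text the excess is half a percentage point, and the larger figures come from p-value criteria that the plan does not mention. Always testing both sexes, which is not faulted here, gives 9.75%.
- **The plan does not claim that boys and girls respond alike.** That is correct. Low power matters only as a caution against reading a pooled result that way.
- **Other remedies exist.** Naming the sex-specific results as the headline would also fix the choice in advance. Defining an important difference would make the rule reproducible, but the choice would still depend on the tested data. Pooling is preferred because the Section 4 hypothesis is not sex-specific and the pooled estimate is more precise.

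What survives is that the stated comparison does not match the design and that the headline Aim 2 estimate is left to the data.

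**Conclusion.** Both parts hold on the text. The mismatch between two waves and three cohorts is certain, though probably un-updated wording. The choice between pooled and sex-specific results is data-driven and has no stated criterion. How far it affects error is conditional. With 12 per sex, no true change and two-sided tests, it is about 5.5% or 7.9% to 10.5% per outcome if either sex counts, depending on the criterion. It is about 4% to 5% if both sexes must be significant, and does not apply if only estimates with intervals are reported.

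This is a single-arm pilot of preliminary efficacy, and nothing in the documents ties the next study to a p-value in one sex. The consequence is for interpretation. The change is worth making as a modest improvement, not as the repair of a material error-rate failure.

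**What to change.** In Section 13:

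1. Replace the references to two waves with three cohorts in the paragraphs for Aims 1, 2a and 2b.
2. State that the pooled mean change with its 95% confidence interval is the headline result for each Aim 2 outcome, whatever sex difference is observed.
3. Always report the change in boys, the change in girls and their difference, each with a 95% confidence interval, as secondary and descriptive results.
4. Keep the cohort-specific analysis triggered by Aim 1, and report it beside the pooled result.
5. Align Sample Size Considerations: remove the conditional wording on combining the sexes, and say that the separate-sex sizing describes the secondary analyses.

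The cost is wording only; data collection and enrolment do not change. The downside is that the sex-specific analyses used to size the study become secondary, although their estimates are still reported. In return, the headline interval is narrower than an interval within one sex.

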## **10. STUDY ENDPOINTS\***

The measures used in this project are designed to test the feasibility of the intervention and assess its preliminary efficacy for increasing physical literacy and food literacy in adolescents with ID. Measures of physical literacy and food literacy will be obtained **at baseline and after the 12-week intervention.**

Below are brief descriptions of the measures – these are also described in the grant application, which includes bibliographic references for validated measures.

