### **(3) Measures of Physical Literacy**

- *Movement Skills.* **Test of Gross Motor Development-Third Edition (TGMD-3)** will be used to measure movement skills. The TGMD-3 assesses 13 fundamental motor skills that are divided into two sub-scales: 1) locomotor skills and 2) ball skills. The TGMD-3 is a direct observation skill assessment with 3-5 performance criteria for each skill. The following skills from the TGMD-3 will be assessed: skipping, two-foot jumping, one-foot hopping, sideways sliding, overhand throw, underhand throw, catch, hand dribble, and kick. The TGMD-3 will be administered via Zoom (i.e., remotely) at baseline and post-12 weeks. Specifically, a trained tester will provide verbal instructions and demonstrations for each skill on the TGMD during a recorded Zoom meeting. A parent/guardian will assist by ensuring that the participant’s performance is clearly visible in the frame of the camera and may provide prompting and/or clarification to their child. Additionally, instructional videos for each TGMD skill will be provided to the participants and parents in advance for them to review and practice before the testing session. It should take approximately 30-40 minutes to administer. A trained professional will review and code the video-recorded TGMD-3 performance on each skill and provide a score at baseline and post-test.

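### Every power figure in Section 13 comes from CAMSA, which the plan mentions nowhere else, and two of the six named Aim 2 tests use scores that Section 10 does not describe

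*Combined protocol and SAP*

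**What the plan says.** **Sample size (Section 13, Sample Size Considerations).** "We established the sample size for this pilot study based on the aforementioned total and skill score on the CAMSA". Using estimates from typically developing adolescents, the section takes a 15% improvement as 6.63 points (total) and 3.66 points (skill). It gives the SD of the change as 5.19 and 3.10, and correlation coefficients of 0.91 and 0.80. It then says that 12 boys and 12 girls, analysed separately, "has, at an alpha level of 0.05, 80% power to assess a difference of 15% in total score and 15% in skill score". Fifteen per sex are to be enrolled. If the sexes are pooled, "we would have adequate power to detect changes of the magnitude ~5% total and skill scores".

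**Outcomes (Section 10).** The movement measure is TGMD-3: "The TGMD-3 will be administered via Zoom (i.e., remotely) at baseline and post-12 weeks". The measure under the desire heading is the CAPL-2 adequacy and predilection total, scored 0 to 6. On timing, "Measures of physical literacy and food literacy will be obtained" at baseline and after the 12 weeks. The section calls its descriptions brief and adds that "these are also described in the grant application, which includes bibliographic references for validated measures".

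**Tests (Section 13).** Each is a one-sample paired t-test of change against zero. For Aim 2a there are "separate tests for TGMD-3 scores, PSI-VSF-ID physical self-concept, and CSAPPA score". For Aim 2b: "We will use a 1-sample (paired) t-test to test Food Knowledge, Food Skill Master, and Dietary Behavior scores".

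**The concern.** The sample-size text presents CAMSA as a measure already introduced and ties it to Aim 2a, but nothing before or after describes it. A reader will take 80% power for 15%, and about 5% pooled, as properties of this trial's movement outcome. They are not, and they cannot be converted to TGMD-3 points because no SD of change for TGMD-3 is given.

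Two smaller mismatches sit in the same section. The desire test names a score that Section 10 does not describe, while the desire score that Section 10 does describe has no named test. The food-skill test cannot be reproduced from this document. Section 4 predicts significant improvements and Section 13 plans hypothesis tests. If the labels are not settled before analysis, the choice of which score counts as desire or food skill is left until the data are in.

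**Working it through.** **1. The plan's own figure at n=12 per sex.** Inputs from Section 13: change Δ = 6.63 (total) and 3.66 (skill); SD of change 5.19 and 3.10; alpha 0.05. Sidedness is not stated, so two-sided is assumed. Power = P(T > t(0.975, n−1)), where T is noncentral t with n−1 df and noncentrality (Δ/SD)·√n.

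- Total: 6.63/5.19 = 1.277; ×√12 = 4.43; critical value 2.201; power 98.0%.
- Skill: 3.66/3.10 = 1.181; ×√12 = 4.09; power 96.0%.
- Smallest n for 80%: 7 (total) and 8 (skill).

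The stated 12 at 80% is not reproduced; one-sided power is higher still (99.4% and 98.5%). A normal formula for two independent groups, 2(1.96+0.84)²(SD/Δ)², gives 9.6 and 11.3, so 10 and 12 per group. That returns 12, but it is not the planned test, and the document does not say it was used.

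**2. The pooled figure.** Let d be the standardised change detectable with 80% power. In percent it is 15 × d × SD/Δ.

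| n | d (two-sided) | Total | Skill | Power for a 5% change (total / skill) |
|---|---|---|---|---|
| 24 | 0.597 | 15×0.597×5.19/6.63 = 7.0% | 15×0.597×3.10/3.66 = 7.6% | 52% / 46% |
| 30 | 0.529 | 6.2% | 6.7% | 62% / 55% |

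One-sided, the detectable changes are 6.1% and 6.6% at n=24, and 5.5% and 5.9% at n=30. If 5.19 and 3.10 were single-occasion SDs, the SD of change would be SD·√(2(1−r)), or 2.20 and 1.96, and n=24 would detect 3.0% and 4.8%. The section, however, calls them SDs of the change.

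**3. What n does detect, on any scale.** Detectable change at 80% power and alpha 0.05, in SDs of change. The 95% CI half-width is t(0.975, n−1)/√n. The 10% dropout in Section 24 gives 30×0.90 = 27.

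| n | Two-sided | One-sided | Half-width |
|---|---|---|---|
| 12 per sex | 0.89 | 0.77 | 0.64 |
| 15 per sex | 0.78 | 0.68 | 0.55 |
| 24 pooled | 0.60 | 0.52 | 0.42 |
| 27 pooled | 0.56 | 0.49 | 0.40 |
| 30 pooled | 0.53 | 0.46 | 0.37 |

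**4. Named tests against Section 10.**

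| Test in Section 13 | Described in Section 10? |
|---|---|
| TGMD-3 | Yes |
| PSI-VSF-ID | Yes |
| CSAPPA | No; the desire measure described is the CAPL-2 total |
| Food Knowledge | Yes |
| Food Skill Master | No |
| Dietary Behavior | Yes |

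Four of six match an instrument. This count is of instruments and does not show that every score is fully defined. CSAPPA and Food Skill Master occur only in the analysis text, and CAMSA only in the sample-size text.

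Section 13 lists ability, confidence and desire, then three tests in the same order, so CSAPPA falls where the desire score belongs. Food preparation skill is part of Aim 2b in Section 4, and Section 16 refers to measures of it, but neither place describes one.

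**The case against.** This is a single-arm pilot whose first aim is feasibility. Section 13 says openly that the CAMSA estimates come from typically developing adolescents, and describes the calculation in the past tense. Section 9 records a COVID suspension and a new plan, so leftover text is a plausible explanation. The CSAPPA label looks like the same kind of leftover, since a desire measure is described and given. For food skill, Section 10 calls itself brief and points to the grant application, which is not available here and may hold the instrument.

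Most of this stands as explanation and limits the weight of the point. It does not remove it: the sample-size text still presents CAMSA as a current Aim 2a measure, and its two power claims still describe nothing the plan collects. The pointer says the measures are also described in the grant, so it does not excuse Section 10 from describing a score that Section 13 tests.

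A reader might infer that the trial is underpowered or that n must rise. The documents do not support that: on the section's own inputs, 12 per sex is more than enough for 15% on CAMSA, and power for TGMD-3 is unknown rather than shown to be low. A reader might also infer that desire or food skill is not measured at all. Desire plainly is. For food skill, what is shown is a missing description, not a missing measure.

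**Conclusion.** The sample-size statement is wrong as written and should be corrected. None of its power figures refers to an outcome the plan describes. Even for CAMSA, the planned paired test gives 98% and 96% at n=12 where the plan states 80%. The pooled detectable change is 6.2% to 7.6% across n=24 to 30, against the stated figure of about 5%. These results assume a two-sided 0.05 test and take the stated SDs as SDs of change. One-sided testing narrows the pooled gap (5.5% and 5.9% at n=30), and only a reading of the SDs that the text contradicts would bring the detectable change below 5%.

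The two label problems are secondary. CSAPPA is probably a stale name, although the documents never link it to CAPL-2. The food-skill test lacks a description in this document. No Aim 2 test is blocked except possibly food skill.

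**What to change.** **Sample Size Considerations.** Keep CAMSA only as the historical basis for choosing n. State that the movement outcome is now TGMD-3. Withdraw the 15% and 5% statements as claims about this trial. State sidedness and what n detects. If two-sided, for example: 'With a paired t-test at two-sided alpha 0.05 and 80% power, the detectable change is 0.89 SD of change at n=12 and 0.78 at n=15 per sex, and 0.60 at n=24, 0.56 at n=27 and 0.53 at n=30 pooled; the corresponding 95% CI half-widths are 0.64, 0.55, 0.42, 0.40 and 0.37 SD.' If one-sided, the detectable changes are 0.77, 0.68, 0.52, 0.49 and 0.46. A TGMD-3 figure in points needs an SD of change, stated as an assumption.

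**Aim 2a.** The sponsor should confirm which desire score is meant. If it is the CAPL-2 adequacy and predilection total (0 to 6), name it in place of CSAPPA.

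**Aim 2b.** Describe the food-skill instrument and its score in Section 10. If it is no longer given, remove it as an evaluated outcome from Sections 4, 13 and 16.

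**Cost.** There are no new participants or visits, and n is unchanged. The detectable change is no longer a percentage of a named score. Describing food skill needs new text in Section 10. Removing it is more than a wording change, because it concedes that a stated part of Aim 2b is not evaluated.

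### The only power statement is for the CAMSA, which this protocol does not collect, so the stated power applies to no planned test, including the TGMD-3 test of Aim 2a

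*Combined protocol and SAP*

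**What the plan says.** Sample Size Considerations in Section 13 is the only place where the protocol gives power figures. The sample size was set "based on the aforementioned total and skill score on the CAMSA (Specific Aim #2a"), using data from typically developing adolescents. The targets are improvements of 6.63 points (total) and 3.66 points (skill), each described as a 15% change. On variability it says: "We estimated the standard deviation of the change in the measure (5.19 total; 3.10 skill) and the interclass correlation coefficient". Those coefficients are 0.91 for the total and 0.80 for the skill score. On the CAMSA in the target population it says: "Estimates on the CAMSA from adolescents with ID are unavailable in the literature".

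Two power claims follow:
- By sex, for a change of 15% in either score: "A sample size of 12 boys and 12 girls has, at an alpha level of 0.05, 80% power to assess a difference of 15"%.
- Sexes combined: "we would have adequate power to detect changes of the magnitude ~5% total and skill scores".

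Enrolment is 15 boys and 15 girls, to allow for attrition and missing data. Section 24 allows for 10% dropout.

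The movement outcome elsewhere is the TGMD-3. Section 10(3) describes it, Section 11 schedules it at enrolment, and Section 26 lists it as study data. For Aim 2a, Section 13 says "we will conduct 1-sample paired t-tests for change (against the null hypothesis of a change of zero"). The scores to be tested, one by one, are those of the TGMD-3, the PSI-VSF-ID and the CSAPPA.

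**The concern.** The sample-size paragraph treats the CAMSA as already introduced and assigns it to Aim 2a, but in the supplied text it appears only in that paragraph. It is not among the measures in Section 10 and not among the tests in Section 13. Every figure in the power statement is therefore on the scale of an instrument that the study does not use. No SD of change, target change or power is given for the TGMD-3 or for any other score to be tested.

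This matters because the protocol justifies n by power, predicts significant improvements in physical literacy (Section 4) and plans hypothesis tests. A non-significant TGMD-3 result could be read against an 80% figure that does not belong to it.

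**Working it through.** **1. Which measure is powered, and which is tested**

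| Section | CAMSA | TGMD-3 |
|---|---|---|
| 10(3), measures | not listed | listed, baseline and 12 weeks |
| 11, enrolment procedures | not listed | administered |
| 13, Aim 2a tests | not listed | paired t-test of change |
| 13, sample size | sole basis | not mentioned |
| 26, data collected | not listed | listed |

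The CAMSA figures cannot be carried across, because the documents give no conversion between the scales. An SD for the full TGMD-3 could not simply be substituted either: the test has 13 skills, and Section 10(3) names nine for assessment ("skipping, two-foot jumping, one-foot hopping, sideways sliding, overhand throw, underhand throw, catch, hand dribble, and kick"), administered over Zoom.

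**2. The plan's own figures on its own inputs**

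Inputs (Section 13): targets 6.63 and 3.66; SDs 5.19 and 3.10; ICCs 0.91 and 0.80; alpha 0.05. Sidedness is not stated, so two-sided is assumed. Results are given as total/skill.

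Implied baselines: 6.63/0.15 = 44.2 and 3.66/0.15 = 24.4. A 5% change is therefore 2.21 and 1.22 points.

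Paired t-test: power = P(T > t with n−1 df at 0.975), where T is noncentral t with n−1 df and noncentrality (change/SD of change) × √n.

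*Literal reading: 5.19 and 3.10 are SDs of change.*
- 15% change: 6.63/5.19 = 1.277 and 3.66/3.10 = 1.181. Power at n=12 is 98%/96%, against the stated 80%. An n of 7/8 would already give 80%.
- 5% change: 2.21/5.19 = 0.426 and 1.22/3.10 = 0.394. Power is 52%/46% at n=24 and 62%/55% at n=30.
- Change detectable with 80% power: 7.0%/7.6% at n=24 and 6.2%/6.7% at n=30. For example, at n=24 the total score gives 0.597 × 5.19 = 3.10 points, and 3.10/44.2 = 7.0%. One-sided at n=30 it is 5.5%/5.9%.

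*Alternative reading: the SDs are single-occasion values and the ICCs convert them.* SD of change = SD × √(2(1−ICC)).
- 5.19 × √0.18 = 2.20 and 3.10 × √0.40 = 1.96.
- 15% at n=12: over 99.9% for both scores.
- 5%: 99.7%/83% at n=24; over 99.9%/91% at n=30.

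Taken as minimums, both claims hold on this reading. It departs from the wording, which calls the SDs those of the change, but it gives the quoted ICCs a use.

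The closest match to exactly 80% comes from a two-independent-samples t-test (85%/79% at 12 per group). That is not the planned one-group design.

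**3. What n supports for any paired outcome**

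Two-sided 0.05 paired t-test, in units of the SD of change. The CI half-width is t(0.975, n−1)/√n.

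| n | Change detectable with 80% power | 95% CI half-width |
|---|---|---|
| 12 (one sex, as planned) | 0.89 | 0.64 |
| 24 (both sexes) | 0.60 | 0.42 |
| 27 (30 less 10%) | 0.56 | 0.40 |
| 30 (all enrolled) | 0.53 | 0.37 |

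These need no instrument-specific input. Turning them into TGMD-3 points needs an SD of change that the documents do not give.

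**The case against.** The best defence is that this is a pilot. Feasibility is Aim 1, Aim 2 is preliminary efficacy, and 95% confidence intervals for change are planned and will show the uncertainty. A pilot does not need a power figure for every test, and n, measures and tests are unaffected. All of that stands, and it limits the consequence. It does not make the existing power claims apply to this study.

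The paragraph may also be text that was not harmonised with later changes. The CSAPPA score in the Aim 2a analysis is likewise absent from the Section 10 measures. Section 10 points to a grant application for further description of the measures, and the CAMSA may be described there. The documents do not settle this. Even if it is, the CAMSA is still neither collected nor tested here.

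A reader might infer two stronger conclusions, and neither is supported.
- *The pilot is too small, or TGMD-3 power is low.* No TGMD-3 SD or target is given, so its power cannot be computed in either direction.
- *The power paragraph is wrong however it is read.* It is not. It does not say how the ICCs were used, and with single-occasion SDs both claims hold as minimums. Adequate power is not defined as 80%, the 5% is approximate, and the one-sided figures at n=30 come close to it. What can be said is that the method is under-described and that the pooled claim falls short on the literal wording.

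**Conclusion.** The point holds as a mismatch between the measure used to justify n and the measures collected. The 80% and roughly 5% claims concern the CAMSA and apply to no planned test. This rests on the supplied text alone and needs no calculation.

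The arithmetic is secondary and minor. It depends on a two-sided 0.05 test and on reading the SDs as SDs of change. On those terms, 80% at 12 per sex is conservative, and the pooled claim has roughly 46% to 62% power across the two scores and n=24 to 30.

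The paragraph should be corrected because it states a property that the design has not been shown to have. It is a correction to the justification, with no reason to change the sample size, outcomes or tests.

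**What to change.** Keep n=30. In Sample Size Considerations:

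1. State that the CAMSA calculation is the historical basis for n and concerns a measure not collected in this protocol.
2. Withdraw the 80% and adequate-power statements as claims for this study.
3. Add text such as:

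> For the TGMD-3 or any other paired outcome, a two-sided 0.05 paired t-test has 80% power for a mean change of 0.89 SD of change with 12 participants of one sex, 0.60 SD with 24 pooled, 0.56 SD with 27 and 0.53 SD with 30. The corresponding 95% confidence-interval half-widths are 0.64, 0.42, 0.40 and 0.37 SD. The SD of change in adolescents with ID is unknown and will be estimated in this study.

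The cost is one paragraph. The study no longer claims sensitivity to a named percentage change, and its sensitivity cannot be expressed in TGMD-3 points until the SD of change has been observed.
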